1.1 Background on Disease

Gastroesophageal Reflux Disease (GERD) is defined as a disorder caused by the repeated reflux of gastric contents into the esophagus, leading to disturbing symptoms and/or complications. The emphasis on the word "disturbing" was proposed by the Asia-Pacific Consensus on the Management of GERD in 2008 to highlight that GERD should be recognized as a disease due to its impact on the patient's quality of life.¹ The global pooled prevalence of GERD is approximately 13.98%, varying from 4.16% in China to 22.40% in Turkey, with the highest reported prevalence in a study conducted in Saudi Arabia (45.4%).² In Korea, the number of GERD patients increased by 11.6%, rising from 4,165,789 in 2016 to 4,650,302 in 2020.³ Additionally, the number of outpatients at Korean medical hospitals increased by 40.4%, growing from 15,776 in 2016 to 22,155 in 2020. In Indonesia, a recent study conducted by Murdani et al. reported that 9.35% of the 278 subjects who participated in the study had GERD.⁴ With the increasing prevalence of GERD worldwide, especially in Indonesia, a scientific consultation meeting with Key Opinion Leaders in Indonesian Gastroenterology is needed to identify the most effective and efficient treatment approaches.

1.2 Background on Existing Treatment

The recent Japanese GERD guidelines, issued by the Japan Society of Gastroenterology in 2021, propose the use of Potassium Competitive Acid Blocker (P-CAB) for both initial and maintenance treatment of mild Erosive Reflux Disease (ERD), in addition to PPI. The guidelines recommend using 4 weeks of P-CAB or 8 weeks of PPI as a first-line treatment for mild ERD. For patients with severe Erosive Reflux Disease, P-CAB is solely recommended as an initial treatment.⁵ In the Seoul Consensus on the Diagnosis and Management of Gastroesophageal Reflux Disease 2020, it is mentioned that the efficacy of potassium-competitive acid blockers (P-CAB) is comparable to proton pump inhibitors (PPI). Therefore, they are recommended as an initial treatment for gastroesophageal reflux disease.⁶

In Indonesia, P-CAB hasn't been included in the Indonesian Guideline for GERD management. This is because Tegoprazan and Vonoprazan were recently launched in Indonesia (the latest Indonesian guideline for GERD is from 2014 with a small revision in 2019), and PPIs continue to be used as the first-line treatment.⁷ Therefore, it is imperative for us to ascertain the necessity of Potassium Competitive Acid Blocker (P-CAB) as the latest treatment for gastric acid-related conditions in Indonesia through comprehensive consultations with Key Opinion Leaders (KOLs) in Indonesian Gastroenterology. This initiative is anticipated to yield invaluable insights guiding our strategic approach to future developments. Furthermore, given the recent introduction of P-CAB in Indonesia, it is of utmost importance to align our efforts with the interests of esteemed KOLs in Gastroenterology to ensure the timely update of the most recent version of the Indonesian Gastroesophageal Reflux Disease (GERD) management guideline. In this specific context, Fexuprazan may assume a pivotal role in shaping the afore mentioned guideline. Employing this systematic approach, our primary objective is to glean insightful perspectives on our product from distinguished Indonesian Gastroenterologist KOLs, enabling us to meticulously formulate a medical strategy that positions our offerings optimally within the Indonesian market.

1.3 Study Drug Profile

Fexuprazan is an antiulcer drug of APA class with a low molecular weight developed by Daewoong Pharmaceutical Co., Ltd. and has a unique chemical structure in comparison with other existing compounds. Fexuprazan has the mechanism of action that inhibits secretion of gastric acid by controlling potassium-dependently and reversibly H⁺ and K⁺ -ATPases within gastric parietal cells. Strong gastric acid secretion inhibition was confirmed in various acid secretion inhibition activity assessments performed in an in-vivo Fexuprazan study using a pylorus ligated rat model, lumen perfused rat (LPR) model, and heidenhain pouch dog (HP-dog) model. Also, the anti-ulcer efficacy of Fexuprazan was confirmed in reflux esophagitis and indomethacin-induced gastric injury model. Additionally, the possibility of oral administration was confirmed by analyzing the pathway of absorption, distribution, metabolism, and excretion via oral administration and the margin of safety was identified through toxicity tests in rodents/non-rodents.⁹

1.4 Prior Study Results

1) Phase 1 Study (DW_FEXUPRAZAN001)

A first in human study (FIH) in Korea was conducted in healthy male volunteers. In a single ascending dose study (n = 72), a single dose of 10, 20, 40, 80, 160, and 320 mg of Fexuprazan was administered in a fasted state with its corresponding dose of placebo in a double-blind manner to assess the safety, tolerability, and pharmacokinetics/pharmacodynamics and 20 and 40 mg of Esomeprazole were used as an active control to compare pharmacodynamic results with Fexuprazan.

To determine the impact of food, 160 mg was studied in a single dose and crossover study. No clinically significant change was found in physical examination, laboratory tests, vital signs, and electrocardiogram, the safety and tolerability endpoints. No SAE occurred and all AEs that occurred were mild (CTCAE 4.0 grade = 1) and were recovered without any special

treatment. A total of 7 adverse drug reactions (ADRs) with suspected causal relationship to Fexuprazan occurred which were epigastric discomfort, dyspepsia, and nausea (1 case each); vomiting and headache (2 cases each). Pharmacokinetic exposure of Fexuprazan oral administration increased more than dose proportionally (Supra-proportionality). In the assessment of pharmacodynamics based on the measurements of intragastric pH for 24 hours after administration of the investigational product, acid secretion within the stomach was inhibited more rapidly after a single administration of Fexuprazan than PPI, and the time during which intragastric pH remained ≥ 4 increased with dose escalation, indicating that gastric acid secretion inhibitory effect continued until nighttime with once-daily dosing. When administering Fexuprazan 160 mg before/after meal, no significant pharmacokinetic/pharmacodynamic change caused by food was observed.

In 7-day multiple ascending dose study (n = 48) conducted at doses of 20, 40, 80, and 160 mg after the single dose study, the safety and tolerability were confirmed for all doses. No SAE occurred and all AEs that occurred were mild (CTCAE 4.0 grade = 1) and were recovered without any special treatment. A total of 6 ADRs that were suspected to be causally related to Fexuprazan occurred which were abdominal distension, abdominal pain, skin exfoliation, headache, abdominal discomfort, and blood creatine phosphokinase increased (1 case each). After multiple doses of Fexuprazan during 7 days, the pharmacokinetic exposure increased dose-proportionally and the accumulation ratios resulting from multiple dosing were $C_{max} = 0.91$ to 1.24 and $AUC_{tau} = 0.93$ to 1.47 . In the pharmacodynamic assessment, the percentage of time during which pH remained ≥ 4 in 24 hours was slightly increased after multiple dosing compared to single dosing, and Fexuprazan 40 mg showed the equivalent level of pharmacodynamics as Esomeprazole 40 mg.

2) Phase 2 Study (DW_FEXUPRAZAN002)

A multi-center, randomized, double-blind, active-controlled, phase 2, therapeutic exploratory study was conducted to evaluate the efficacy and safety of Fexuprazan by dose in patients with erosive gastroesophageal reflux disease in Korea.

In a total of 211 subjects, the results of having administered Fexuprazan 20 mg, 40 mg, 80 mg or Esomeprazole 40 mg once daily before meals for up to 8 weeks were as follows.

The proportions of subjects (FAS set) with mucosal breaks completely healed by Week 8 after administration of the IP, the primary efficacy endpoint, was 93.88% (46/49 subjects) in the Fexuprazan 20 mg group, 92.16% (47/51 subjects) in the Fexuprazan 40 mg group, 95.65% (44/46 subjects) in the Fexuprazan 80 mg group, and 97.92% (47/48 subjects) in the Esomeprazole 40 mg group. Since the lower limits of 95% confidence intervals for the differences in proportions of subjects with mucosal breaks completely healed between each Fexuprazan dose group and Esomeprazole 40 mg group were all larger than the non-inferiority margin of -15%, the effect of Fexuprazan treatment groups was confirmed to be non-inferior compared to the Esomeprazole 40mg group. In the assessment on major symptoms (heartburn and acid regurgitation) based on the diary of subjects, the secondary efficacy endpoint, the Fexuprazan groups showed symptom-alleviating effect in comparison with the Esomeprazole 40 mg group. In particular, the Fexuprazan 40 mg showed statistically significant difference in some assessments.

The 'percentages (%)' of subjects without any major symptoms during 7 days' after starting the IP administration were 14.29% in the Fexuprazan 20 mg group, 21.57% in the Fexuprazan 40 mg group, 19.57% in the Fexuprazan 80 mg group, and 12.50% in the Esomeprazole 40 mg group, indicating no significant difference compared to the Esomeprazole 40 mg group. However, the 'percentages (%)' of days free of any major symptoms during 7 days' after starting the IP administration were 32.14% in the Fexuprazan 20 mg group, 43.98% in the Fexuprazan 40 mg group, 37.89% in the Fexuprazan 80 mg group, and 28.27% in the Esomeprazole 40 mg group, indicating significant difference between the Fexuprazan 40 mg group and the Esomeprazole 40 mg group (p=0.0463). When the results of above were separately analyzed by dividing into daytime and nighttime, the 'percentages (%)' of daytime free of any major symptoms for 7 days' indicated no statistically significant difference between the Fexuprazan groups and the Esomeprazole 40 mg group. However, the 'percentages (%)' of nighttime free of any major symptoms for 7 days' were 41.96% in the Fexuprazan 20 mg group, 55.18% in the Fexuprazan 40 mg group, 48.76% in the Fexuprazan 80 mg group, and 33.63% in the Esomeprazole 40 mg group, indicating significant difference between the Fexuprazan 40 mg group and the Esomeprazole 40 mg group (p=0.0083). The 'percentages (%)' of days free of any major symptoms for 8 weeks' indicated the same tendency with 49.41% in the Fexuprazan 20 mg group, 59.41% in the Fexuprazan 40 mg group, 55.65% in the Fexuprazan 80 mg group, and 42.88% in the Esomeprazole 40 mg group, indicating a significant difference between the Fexuprazan 40 mg group and the Esomeprazole 40 mg group (p=0.0283). When the results were separately analyzed by dividing into heartburn and acid regurgitation which were the major symptoms, the effect on the symptom of acid regurgitation showed no significant difference, but the percentage of days free of heartburn (7 days and 8 weeks) showed significant difference between Fexuprazan 40 mg and Esomeprazole 40 mg (p=0.0326 for the percentage of days free of heartburn during 7 days; p=0.0264 for the percentage of days free of heartburn during 8 weeks). Therefore, all Fexuprazan groups showed rapid improvement of symptoms and acid secretion inhibitory effects sustained until the nighttime. Especially, Fexuprazan 40 mg showed significant improvement of symptoms compared to Esomeprazole. The assessment of quality of life (GERD-HRQL) confirmed that the quality of life from symptoms were improved in all Fexuprazan groups.

The incidences of AEs and ADRs showed no statistically significant difference among treatment groups, and the events were all mild in severity and recovered without sequelae. One (1) case of moderate herpes zoster was reported as an SAE in the Esomeprazole 40 mg group, and no serious ADR, and AE and ADR resulting in death occurred during this study.

1.5 Assessment of Benefits and Risks

Reportedly, PPIs, the first-line therapy for diseases related to gastric acid secretion, takes 3 days or longer to make improvements in major symptoms (acid regurgitation and heartburn)⁸; their acid secretion inhibitory effects do not last until the nighttime¹⁰; and the genetic polymorphism of CYP2C19¹¹ causes variations in individual efficacy. Moreover, the regimen is restricted to be taken before a meal. Currently, drugs with APA mechanism are being developed to overcome these limitations of PPIs. The first phase I clinical study in healthy male adults confirmed that, unlike other PPIs that are activated under a strong acidic condition, Fexuprazan had a fast onset time and showed its acid secretion inhibitory effect that persisted until the nighttime since it had a reversible mechanism of action without activation by inhibiting the proton pump. Besides, since food does not have any significant effect on absorption of the drug, the patients can take the drug with or without having a meal, and it is expected that the patient's convenience of taking the drug can be improved.

[figure not shown]
In the phase 2 study conducted in patients with erosive gastroesophageal reflux disease, healing of mucosal breaks in all Fexuprazan groups was non-inferior to the Esomeprazole 40 mg group, and no AE and ADR was noticeable in terms of safety. Also, Fexuprazan showed an effect of alleviating acid regurgitation and heartburn which are the major symptoms of gastroesophageal reflux disease during the treatment period.

Thus, the benefit expected from administration of Fexuprazan in patients with erosive gastroesophageal reflux disease, one of gastric acid secretion related diseases is considered to outweigh the risk, and a multi-center, randomized, double-blinded, active-controlled, phase 3, therapeutic confirmatory study was planned to assess the efficacy and safety of Fexuprazan in patients diagnosed with erosive gastroesophageal reflux disease.

[figure not shown]
1.6 Rationale for Selection of Doses

A dose-finding study in patients with erosive gastroesophageal reflux disease confirmed that the Fexuprazan 40 mg had a similar safety profile to the Esomeprazole 40 mg group, it was non-inferior to the Esomeprazole 40 mg group for the proportions of subjects with mucosal breaks completely healed by Week 8, primary efficacy endpoint, and at the same time, it had a significant improvement of symptoms compared to the Esomeprazole 40 mg group.

For the 'percentages (%) of subjects without the major symptoms for 7 days' and 'percentages (%) of subjects without the major symptoms during 8 weeks' after initiation of the IP administration, the effect of Fexuprazan 20 mg was similar to Esomeprazole 40 mg. The percentages (%) of subjects without the major symptoms for 7 days and 8 weeks in the Fexuprazan 40 mg group and the Fexuprazan 80 mg group tended to be higher than the Esomeprazole 40 mg group. Therefore, rapid improvement of symptoms is expected from the Fexuprazan 40 mg or higher which is deemed to be based on the advantage of Fexuprazan with APA mechanism in which activation of proton pump is unnecessary whereas the PPI takes 3 days or longer from the drug administration to the onset of action.

In addition, 'percentages (%) of days free of any major symptoms for 7 days' and 'percentages (%) of days free of any major symptoms for 8 weeks' tended to be higher in all Fexuprazan groups compared to the Esomeprazole 40 mg group. In particular, the Fexuprazan 40 mg group showed a statistically significant result compared to the Esomeprazole 40 mg group.

Percentages (%) of days free of each symptom for 7 days

[figure not shown]
Protocol No.DW_DWP1401262001

Protocol Version, 2.1

23 / 55 page

Version date 2024-06-19

When the results were analyzed by dividing into daytime and nighttime, the percentages of daytime for 7 days were not significantly different between the Fexuprazan dose groups and the Esomeprazole 40 mg group. However, Fexuprazan 40 mg showed a statistically significant difference in nighttime heartburn and heartburn + acid regurgitation compared to the control group. Therefore, it is considered that the difference in the symptom improvement resulted from acid secretion inhibitory effects sustained until the nighttime with Fexuprazan 40 mg once daily dosing. Also, no significant difference was seen from the daytime results for 8 weeks compared to the Esomeprazole 40 mg group, except for heartburn symptom. However, the Fexuprazan 40 mg showed statistically significant difference in all nighttime symptoms (heartburn, acid regurgitation, heartburn + acid regurgitation) for 8 weeks compared to the Esomeprazole 40 mg. Therefore, it can be said that Fexuprazan 40 mg significantly improves the symptoms during the treatment period because it has a rapid onset of action compared to the control group and its acid secretion inhibitory effects last until the nighttime.

With this study, it is intended to develop an acid pump antagonist that can address the unmet medical needs of PPIs which are slow onset of action and nocturnal acid rebound. In the phase 2 study, the assessment of primary efficacy endpoint showed that all Fexuprazan groups were non-inferior to the control group and did not show difference among the dose groups, but it is expected that Fexuprazan 40 mg and higher dose would show difference in symptom improvement. Therefore, the phase 3 dose was set at Fexuprazan 40 mg to confirm the efficacy and safety in patients with erosive gastroesophageal reflux disease.

2 Study Objective

This study is to evaluate symptom relief after using Fexuprazan 40 mg compared to Esomeprazole 40 mg for patient with Gastroesophageal Reflux Disease (GERD).

3 Study Population

3.1 Target Number of Subjects

The number of subjects to demonstrate non-inferiority of the study group compared to the control group with 80% power using a non-inferiority margin of -0.1 at one-sided significance level of 2.5%, considering a 20% dropout rate, a total of 134 subjects will be needed.

3.2 Inclusion Criteria

Subjects must meet all the following criteria:

- 1) Male and female adults aged 18 to 60 years at the date of the written informed consent form.
- 2) Those who had experienced heartburn and/or acid regurgitation confirmed with:
 - a. GERD-Q Score >7 and
 - b. People who have experienced heartburn symptoms > 3 days within the last 7 days, or
 - c. People who have experienced acid reflux (symptom of acid reflux or back flowing of contents from stomach into the esophagus) > 3 days within the last 7 days
- 3) Those who could understand the provided information and able to fill out the questionnaire and subject diary.

4) Those who voluntarily decided to participate in the study and wrote the informed consent form.

3.3 Exclusion Criteria

[Digestive system related]

- 1) Those who have been diagnosed with inflammatory bowel disease (Crohn disease, ulcerative colitis, etc.), primary esophageal motility, or pancreatitis.
- 2) Those who had a surgery to reduce gastric acid secretion or gastric or esophageal surgery (e.g., gastrotomy, mucosal resection, etc.), except appendectomy, cholecystectomy, or endoscopic polypectomy of benign polyps.
- 3) Those who had warning symptoms of malignant gastrointestinal tract such as odynophagia, severe dysphagia, bleeding, weight loss, anemia, or bloody stool.
(But those who have additional warning symptoms besides typical symptoms of gastroesophageal reflux disease may be included if the result of endoscopy for verifying whether to have tumor is negative.)

[Medical history]

- 4) Those who had a history of clinically significant disease of hepatic, renal, endocrine, hemato-oncologic, or urinary system.
- 5) Those who had history malignant tumor in the last 5 years.
(But in case of malignant tumors except digestive malignant tumor, subjects completely healed for 5 years without recurrence are allowed to enroll.)
- 6) Those who had a history of psychosis, illegal drug or alcohol abuse.
- 7) Those who had a known acquired immunodeficiency syndrome (AIDS) or hepatitis infection, including HBsAg+ or hepatitis C virus (HCV)-antibody-positive or virus carriers.
(But the participant may be included in the study if he/she is HCV-RNA-negative). Rapid test screening will be done if there are no previous result.
- 8) Those who had hypersensitivity or history of clinically significant hypersensitivity reaction to investigational product.

[Medication history/treatment history]

- 9) Those who received concomitant prohibition drugs within 2 weeks prior or need continuous treatment during the clinical study^{*)}
*) Those who meet the inclusion criteria following a sufficient wash-out period (2 weeks for NSAIDs with a half-life of > 24 hours) after taking the following drugs can be enrolled
 - a. Non-steroidal anti-inflammatory drugs (aspirin, etc.) and acetaminophen: a low dose of aspirin (≤ 100 mg/day) which has been administered for the purpose of prevention before participating in the study is allowed: acetaminophen administration is allowed up to 4 g/day and does not exceed 5 days in 4 weeks.
 - b. Acid suppressive drugs: Proton pump inhibitors (PPIs), PCAB, H2 receptor antagonists, anti-gastrin agents
 - c. Cholinergic drugs, anticholinergic drugs, and antispasmodics
 - d. Psychotropic drugs: Antipsychotics drugs, antidepressants, antimanic drugs, antianxiety drugs, and hallucinogenic agents, etc.
 - e. Steroids (allowed if used in a local application)
 - f. Antithrombotic drugs (antiplatelet drugs and anticoagulants)
 - g. Mucoprotective drugs
- 10) Those who need to take any prohibited concomitant medication during clinical study. (Only Antacid and Prokinetic permitted as rescue drug. The use of Antacid and Prokinetic during the study period will be recorded as subject's prior/concomitant medication)
- 11) Those who took the other investigational product within 4 weeks prior to administration of investigational product.
(But it is possible to enroll in the study [i.e., observational study, retrospective study] that doesn't affect this study's efficacy and safety as determined by the investigator.)

[Laboratory tests]

- 12) At screening, those who had
 - a. serum alanine aminotransferase (ALT), aspartate aminotransferase (AST), or total bilirubin levels $\geq 2 \times$ upper limit of normal
 - b. serum creatinine or BUN $\geq 2 \times$ upper limit of normal

[Others]

- 13) Pregnant or breast-feeding women
- 14) Those who do not consent to use appropriate contraceptive methods during the study.
Appropriate contraceptive methods for patients or their partners:
- For Male subject: to use barrier method such as male condom and surgical sterilization such as vasectomy;
- For Female subject: to use 1) hormonal contraceptive such as Intrauterine system : intrauterine hormone-containing system, implant, injection, contraceptive pills, or 2) non hormonal contraceptive such as Intrauterine system : copper loop,

barrier method : female condom, diaphragm or cervical cap, or surgical sterilization : tubectomy.

15) In the opinion of the investigator, those who were unsuitable for any reason.

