Study Methodology	
Subjects will be provided a written informed consent to participate in the study and then undergo any screening. If a subject is taking any drug that affects the gastric mucosa at the time of screening, the treatment will be start after washout period of up to 2 weeks. Subjects who meet all of the inclusion criteria and none of the exclusion criteria based on the screening test results will be randomized.
 
Overall, the subjects will receive treatment for a duration of 4 ~ 8 weeks., The subjects will take 1 tablet/capsule of the investigational product (IP) once daily (1 tablet of Fexuprazan 40 mg or 1 capsule Esomeprazole 40 mg according to randomization). Initially, the subject will received the IP for 1 week at Visit 2 (Day 0). Subject will visit the study site at Visit 3 (Day 7 ± 5 days) for early evaluation and will be prescribed for another 3 weeks of IP. Subjects will visit the study site at Visit 4 (Day 28 ± 5 days) to determine healing status through symptom relief. Healed subjects after 4 weeks of treatment will have a Safety Follow-Up (F/U) visit after 2 weeks, while unhealed subjects will continue with an additional 4 weeks of treatment. After unhealed subjects have completed a total of 8 weeks of treatment at Visit 5 (Day 56 ± 5 days), they will have a Safety F/U visit after 2 weeks. (This Safety F/U will be conducted over the phone. If necessary, additional examination and treatment may be performed according to the investigator's judgment.)

Figure 1. Study Schematic

Inclusion Criteria	
Subjects must meet all the following criteria:
 
 1) Male and female adults aged 18 to 60 years at the date of the written informed consent form. 2) Those who had experienced heartburn and/or acid regurgitation confirmed with: 
 ➢ GERD-Q Score >7 and ➢ People who have experienced heartburn symptoms > 3 days within the last 7 days, or ➢ People who have experienced acid reflux (symptom of acid reflux or back flowing of contents from stomach into the esophagus) > 3 days within the last 7 days 3) Those who could understand the provided information and able to fill out the questionnaire and subject diary. 4) Those who voluntarily decided to participate in the study and wrote the informed consent form.

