Inclusion/exclusion criteria ⁹⁾		O						
Prescription of IPs ¹⁰⁾		O	O	O ¹³⁾				
Return of IPs and check of treatment compliance ¹⁰⁾			O	O		O ¹³⁾		O ¹²⁾
Distribution of subject diary ¹⁰⁾			O	O	O ¹³⁾			
Collection of subject diary ¹⁰⁾			O	O		O ¹³⁾		O ¹²⁾
Adverse events			O	O	O	O	O	O ¹²⁾

- 1) Visit 1 and Visit 2 can be conducted on the same day.
- 2) Eligibility of subjects will be assessed based on the results from Visit 2 (GERD-Q result from Visit 1 will be used as the eligibility criteria). However, the results may be replaced with the test results obtained within 7 days prior to Visit 2, if available.
- 3) Gastrointestinal medical history and surgical history will be investigated at Visit 1 regardless of the time of previous occurrence and, for other medical history and surgical history, only those which occurred within 6 months from screening or are ongoing at screening and baseline will be investigated.
- 4) For prior medications, information on drugs administered within 4 weeks from the date of the written consent at Visit 1 will be collected. (Only Antacid and Prokinetic permitted as rescue drug)
- 5) Vital signs: After resting in a sitting position for 5 minutes or longer, blood pressure (diastolic/systolic), pulse rate, and body temperature will be measured.
- 6) The relevant tests can be replaced with the test results obtained from the same institution within 2 weeks from Visit 1, if available.
- 7) Laboratory tests will be conducted to check the inclusion/exclusion criteria and assess the safety (Visit 1, Visit 4, Visit 5, Withdrawal visit, and Safety F/U). At Visit 1, a re-test may also be conducted once according to the investigator's judgment and, in such a case, evaluation will be based on the result of re-test.

① Hematology	WBC with differential count (neutrophil, lymphocyte, monocyte, eosinophil, basophil), RBC, hemoglobin, hematocrit, platelets
② Blood Chemistry	Random blood glucose, ureum, uric acid, AST, ALT, creatinine, total bilirubin
③ Blood Coagulation test	PT, INR, APTT
④ Urinalysis	pH, specific gravity, albumin, bilirubin, glucose, urobilinogen, ketone, nitrite, occult blood, microscopy (urine RBC, urine WBC)

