8.2 Study Schedule Table

	Screening (wash-out)	Treatment 1			Safety F/U ¹¹⁾	Treatment 2 (Unhealed Subject after 4 Weeks of Treatment)	Safety F/U ¹¹⁾	Withdrawal Visit ¹²⁾
Visit	Visit 1 ¹⁾	Visit 2	Visit 3	Visit 4	Visit 4-1	Visit 5	Visit 5-1	
Protocol No.DW_DWP1401262001					30 / 55 page			Protocol Version, 2.1 Version date 2024-06-19

Schedule	Day-14~	Day 0	Day 7	Day 28	Day 42	Day 56	Day 70	
Window	-	-	± 3 day	± 5 day	± 5 day	± 5 day	± 5 day	
Informed consent	O							
Demographic survey	O							
Assessment on symptom questionnaire (GERD-Q) ²⁾	O	O	O	O		O ¹³⁾		O ^{*)}
Quality of Life assessment (GERD-HRQL)		O	O	O		O ¹³⁾		O ^{*)}
Medical and surgical history ³⁾	O	O						
Prior/concomitant medications ⁴⁾	O	O	O	O	O	O	O	O ¹²⁾
Vital signs ⁵⁾	O	O	O	O	O ¹¹⁾	O ¹³⁾	O ¹¹⁾	O ¹²⁾
Physical examination	O	O	O	O	O ¹¹⁾	O ¹³⁾	O ¹¹⁾	O ¹²⁾
Laboratory tests ^{6),7)}	O			O	O ¹¹⁾	O ¹³⁾	O ¹¹⁾	O ¹²⁾
Pregnancy test ^{6),8)}	O	O						
Inclusion/exclusion criteria ⁹⁾		O						
Prescription of IPs ¹⁰⁾		O	O	O ¹³⁾				
Return of IPs and check of treatment compliance ¹⁰⁾			O	O		O ¹³⁾		O ¹²⁾
Distribution of subject diary ¹⁰⁾		O	O	O ¹³⁾				
Collection of subject diary ¹⁰⁾			O	O		O ¹³⁾		O ¹²⁾
Adverse events			O	O	O	O	O	O ¹²⁾

- 1) Visit 1 and Visit 2 can be conducted on the same day.
- 2) Eligibility of subjects will be assessed based on the results from Visit 2 (GERD-Q result from Visit 1 will be used as the eligibility criteria). However, the results may be replaced with the test results obtained within 7 days prior to Visit 2, if available.
- 3) Gastrointestinal medical history and surgical history will be investigated at Visit 1 regardless of the time of previous occurrence and, for other medical history and surgical history, only those which occurred within 6 months from screening or are ongoing at screening and baseline will be investigated.
- 4) For prior medications, information on drugs administered within 4 weeks from the date of the written consent at Visit 1 will be collected. (Only Antacid and Prokinetic permitted as rescue drug)
- 5) Vital signs: After resting in a sitting position for 5 minutes or longer, blood pressure (diastolic/systolic), pulse rate, and body temperature will be measured.
- 6) The relevant tests can be replaced with the test results obtained from the same institution within 2 weeks from Visit 1, if available.

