8.3.3 Questionnaire assessment

- Gastroesophageal Reflux Disease Questionnaires (GERD-Q) (See Appendix 3)
 - The subject will complete the GERD-Q at the screening visit (Visit 1) and Visit 2. The test results from Visit 1 will be used as the basis to determine eligibility for inclusion/exclusion.
 - The subjects who meet the inclusion criteria will complete the GERD-Q at Visit 3, Visit 4, and Visit 5.
- Quality of Life assessment (GERD-Health Related Quality of Life, GERD-HRQL) (See Appendix 4)
 - The subjects who meet the inclusion criteria will complete the GERD-HRQL questionnaire at Visit 2, Visit 3, Visit 4 and Visit 5.^[19, 20, 21]

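### Exclusion 9 requires the inclusion criteria to be met after washout, but the GERD-Q that decides eligibility is the Visit 1 score, which precedes washout for anyone still on an acid suppressant.

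*Combined protocol and SAP*

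**What the plan says.** - **Entry after washout.** Exclusion 9 (section 3.3 and synopsis) bars recent users of prohibited drugs, but its note admits "Those who meet the inclusion criteria following a sufficient wash-out period". The listed drugs include "Acid suppressive drugs: Proton pump inhibitors (PPIs), PCAB, H2 receptor antagonists, anti-gastrin agents".
- **Threshold.** Section 3.2 requires "GERD-Q Score >7 and" heartburn or acid reflux on more than 3 of the last 7 days.
- **Order of events.** The synopsis (Study Methodology) says: "If a subject is taking any drug that affects the gastric mucosa at the time of screening, the treatment will be start after washout". Washout therefore follows screening for these subjects.
- **Which score counts.** Section 8.3.3 schedules the GERD-Q at Visits 1 and 2 and adds: "The test results from Visit 1 will be used as the basis to determine eligibility for inclusion/exclusion". Footnote 2 of the schedule says "GERD-Q result from Visit 1 will be used as the eligibility criteria", and footnote 9 repeats this. Both footnotes judge other eligibility on Visit 2 results.
- **Softening text.** Footnote 2 adds that "the results may be replaced with the test results obtained within 7 days prior to Visit 2, if available". Section 8.3.11 allows one rescreening, at the investigator's discretion and after discussion with the sponsor.
- **Recall.** The GERD-Q form (Attachment 2) asks about the last 7 days.
- **Consequences.** Section 9.1 removes subjects who violate eligibility criteria from the FAS. Sections 9.1 and 13.5 make the same violation a major deviation, which removes them from the PPS, the primary set under section 9.2.1.

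**The concern.** For a subject on an acid suppressant at Visit 1, the two rules call for different measurements. The Visit 1 score describes symptoms on the old drug. The score that exclusion 9 implies describes symptoms off it. If the Visit 1 rule is followed, a patient above 7 on a PPI passes and a patient at 7 or below fails, whatever the score after washout. That is selection on response to the comparator's own class.

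Two things are at stake. One is the population: section 1.2 says PPIs remain first-line in Indonesia, so some such patients can be expected, though no number is given. The other is the analysis sets: the choice of score changes who is an eligibility violator, in an open-label trial. Prior acid-suppressant use is not a randomisation factor (sections 4.4 and 8.3.12) and enters no planned analysis (section 9.2), although section 8.3.5 collects 4 weeks of prior medication.

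**Working it through.** **1. The rules side by side, for a subject on an acid suppressant at Visit 1**

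| GERD-Q at Visit 1 (on drug) | GERD-Q at Visit 2 (after washout) | Section 8.3.3, footnotes 2 and 9 | Exclusion 9 |
|---|---|---|---|
| above 7 | above 7 | eligible | eligible |
| above 7 | 7 or less | eligible | not eligible |
| 7 or less | above 7 | not eligible | eligible |
| 7 or less | 7 or less | not eligible | not eligible |

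Rows 2 and 3 conflict. A row 2 subject already meets the relief definition (GERD-Q below 8, section 8.4.2.1) before the first dose. That subject stays in the FAS under one rule and is removed as a violator under the other.

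**2. The plan's sample size (section 9.4.2)**

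Inputs: control 0.885, study 0.940, margin 0.10, one-sided 0.025, n = 53 per arm, pooled Z-test.

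- s0 = sqrt(2 × 0.9125 × 0.0875 / 53) = 0.0549
- s1 = sqrt((0.885 × 0.115 + 0.94 × 0.06) / 53) = 0.0546
- Power = Φ[(0.055 + 0.10 - 1.96 × s0) / s1] = 0.807, as the plan states (n = 52 gives 0.7998)
- Dropout: 53 / 0.8 = 66.25, so 67 per arm and 134 in total

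The sample size is not in dispute.

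**3. What selection could do (assumed inputs)**

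The documents give no share f of subjects who are PPI failures and no relief rate r for them on esomeprazole. Assume r = 60% and f = 20, 30 or 50%. The control rate is (1 - f) × 0.885 + f × r, which gives 0.828, 0.7995 and 0.7425. The losses are 5.7, 8.55 and 14.25 points.

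*Case A: the true difference in unselected patients is exactly -10 points (78.5% v 88.5%).* The chance that the lower 95% limit exceeds -0.10 is taken as Φ[(study - control + 0.10) / s1 - 1.96], with n = 53. Example for f = 20% when fexuprazan loses nothing: s1 = 0.0766, and Φ[0.057 / 0.0766 - 1.96] = 0.112.

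| f | Fexuprazan loses nothing | Loses half as much | Loses equally |
|---|---|---|---|
| 0 | 2.5% | 2.5% | 2.5% |
| 20% | 11.2% | 5.5% | 2.5% |
| 30% | 19.1% | 7.6% | 2.5% |
| 50% | 40.9% | 12.8% | 2.5% |

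With f = 20% and fexuprazan losing nothing, the first figure becomes 7% at r = 70% and 4% at r = 80%.

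*Case B: the planned advantage of 5.5 points holds and both arms lose equally.* The pooled formula of step 2 gives:

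| f | Study v control | Power |
|---|---|---|
| 0 | 94.0% v 88.5% | 81% |
| 20% | 88.3% v 82.8% | 62% |
| 30% | 85.45% v 79.95% | 56% |
| 50% | 79.75% v 74.25% | 47% |

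The sign of the effect therefore turns on how fexuprazan performs in PPI failures, which the documents do not report.

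**The case against.** A reader might infer that the PPI control is handicapped and that non-inferiority becomes easier to claim. The documents do not support this as a finding. It needs PPI failures to do worse on esomeprazole than on fexuprazan, and no results in such patients are reported. Section 1.5 (CYP2C19 variation, weak night-time control on PPIs) makes it plausible. Section 1.4 points the other way, reporting pharmacodynamics for fexuprazan 40 mg equivalent to esomeprazole 40 mg. This objection stands, which is why the 11 to 41% figures must be read beside the 2.5% column.

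The figures are also not false-positive rates in the patients enrolled. PPI failures are randomised to both arms. Under the loses-nothing assumption the true differences among enrolled patients are 78.5 - 82.8 = -4.3, 78.5 - 79.95 = -1.45 and 78.5 - 74.25 = +4.25 points, all inside the margin. The question there is one of generalising to unselected patients. This stands too.

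Nor are PPI responders always lost: footnote 2 permits a replacement result, and one rescreening is possible. Both are discretionary, and section 8.3.3 and footnote 9 state the Visit 1 rule without the replacement option. They soften the problem without removing it.

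Only subjects on an acid suppressant at Visit 1 are affected, and Visits 1 and 2 may fall on one day. The list also covers P-CABs, and selecting P-CAB failures could work against fexuprazan. Finally, section 9.4.2 names no source population for the 88.5%, so the documents cannot show that selection invalidates it.

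**Conclusion.** The contradiction is certain from the text and should be corrected. It changes who may enter and who is removed from the FAS and PPS as an eligibility violator. The Visit 1 rule, if followed, tends to select on response to the comparator's class.

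A bias in favour of fexuprazan is not established. With 60% relief in PPI failures and a share of 20 to 50%, the results run from no change in the chance of a wrong claim (2.5%) to 11 to 41%, depending wholly on the assumed fexuprazan response. With equal loss the harm is to power instead: 81% falls to between 62% and 47%. The share, the relief rate and the split between arms are all assumptions.

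**What to change.** 1. Reconcile section 8.3.3 and footnotes 2 and 9 (synopsis and section 8.2) with exclusion 9. For any subject who undergoes washout, take both the eligibility GERD-Q and the criterion of symptoms on more than 3 of the last 7 days from the post-washout Visit 2 assessment. Name the same score in sections 9.1 and 13.5 as the one that defines an eligibility violation.
2. Report acid-suppressant use in the 4 weeks before consent by arm. Add a supportive sensitivity analysis of the primary comparison in subjects with none recorded.

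**Cost.** The Visit 2 GERD-Q is already scheduled and prior medication is already recorded, so the change is wording plus one analysis. Eligibility of washed-out subjects is settled only at Visit 2, so expect a few later screen failures.

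**Limits.** The sensitivity analysis will be imprecise. If 30% were prior users, 53 × 0.7 = about 37 per arm remain. At the planned rates the 95% half-width grows from 1.96 × 0.0546 = 10.7 points to 1.96 × sqrt(0.1582 / 37) = 12.8 points, where 0.1582 = 0.885 × 0.115 + 0.94 × 0.06. Also, the synopsis gives washout only as an upper limit ("the treatment will be start after washout period of up to 2 weeks"). A 7-day recall at Visit 2 could still cover days on the old drug, and the revised text should say how such a score is treated.
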